treatment. Based on this longitudinal repeated measurement study design, the preliminary data needed for designing future study include: (1) variance of single measurement, (2) covariance (correlation) among the repeated measurements over time within an individual, (3) level of outcome measurements in patients with and without the treatment.

Missing Outcome Data

Not applicable

Unblinding Procedures

The BJH Investigational Pharmacy will maintain a record of each patient's medical record number and to which arm of the study they were assigned. No member of the vascular surgery investigational team will have access to this information. This will serve to maintain blinding and reduce any unwanted during the trial and subsequent analysis of collected data. Un-blinding of patient data will occur during the interim analysis, and at the end of the study. For un-blinding the pharmacy will then un-blind the study to the investigators such that appropriate conclusions can be made regarding the efficacy of the investigational agent.

Data Handling and Record Keeping

Confidentiality and Security

All patient data and demographic information will be analyzed on computers on the Washington University in St. Louis (WUSTL) network. This network is only accessible through appropriately credentialed employees, physicians, and Washington University of St. Louis medical students. Additionally, data is stored on the WUSTL network drive, with separate encryption levels, only accessible by users granted permissions by the appropriate administrator. This prevents unauthorized users, i.e. those not immediately involved in specific projects, from gaining access to patient sensitive information.

Samples and/or data from this research may be shared with other researchers for future projects. All requests, inclusive of proof of review and approval by the Institutional Review Board as applicable, from potential research collaborators will be reviewed on a case by case basis, in writing, by the Principal Investigator(s) prior to the release of samples/data. The data and/or samples approved for release will then be provided to other investigators and will be de-identified (coded). Only the primary NAC study team members have access to the password-protected link to protect patient confidentiality.

Training

All individuals responsible for handling of patient information and/or the consenting process for this clinical trial have been approved and received appropriate training in line with the standards set for by the Washington University in St. Louis Office of the Vice Chancellor for Research. These individuals may include clinical trial nurse coordinators, clinical nurses, clinical fellows, research fellows, and vascular surgery attendings.

Case Report Forms and Source Documents

N/A

Records Retention

Records will be maintained for at least 7 years following the close of this study.

Study Monitoring

Study Monitoring Plan

Monitoring will be used as a quality control tool to be sure that the study is being conducted as planned and as approved by the institutional IRB. Monitoring activities will include regular communication between the PI and study staff; review of the study processes, procedures, and records; assurance of protocol compliance and verification of the accuracy of data collected by the study team. All data collected for the study will have a reliable source document to verify the source of the data. Review of the data for each enrolled subject will be performed on an ongoing basis by the study team (including participant recruitment, accrual and retention, review of documentation of proper informed consent, source document verification, adverse events identification and reporting activities). Conclusions of the ongoing monitoring activities will be reported to the PI. Ongoing monitoring findings will be evaluated to determine whether additional actions (e.g., training of clinical investigator and site staff, clarification of protocol requirements) are necessary to ensure human subject protection and data quality.

Any incidence of protocol noncompliance and all unanticipated problems will be reported to the IRB in accordance with local policy. The study Principal Investigator will perform continuous monitoring of participant safety based on regular review of adverse events captured in the clinical trial.

The PI will ensure monitoring of the conduct and progress of the study that ensures:

1) important information that may affect the safety or welfare of participants comes to light and is acted upon as quickly as possible, and 2) the validity and integrity of the data. The PI will determine based on ongoing safety review whether the study should continue as planned or should be modified/amended or stopped for safety concerns.

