Aside from smoking cessation and physical exercise, there are currently no known effective medical treatments for patients with advanced non-surgically correctable CLI [13, 21]. In addition, the prevalence of amputations resulting from CLI among diabetic patients is disturbingly high [2]. Based on our recent preclinical studies, we are proposing a pilot clinical trial to further explore the potential therapeutic benefits of NAC in healing extremity amputation stumps in the setting of CLI, plus or minus diabetes. These studies are highly innovative in that they: i) explore a compelling new modality of therapy in a highly vulnerable, but frequently under-represented clinical trial patient population, ii) explore a completely novel and not previously reported NAC mechanism of action on phospholipid synthesis and expression, and iii) represent the potential use of a low-cost, generic pharmacological agent, which would otherwise not be pursued by drug pharmaceutical manufacturers due to low-profit margins. In short, this proposal may establish a conceptual infrastructure for future larger clinical trials exploring the use of NAC in patients with CLI and with and without diabetes, and identify a previously unknown novel mechanism of action for NAC.

We believe that previous literature supporting the role of NAC in augmenting compensatory tissue perfusion raises the possibility that this may be an advantageous therapeutic agent to favorably alter the tissue lipidomic profile of diabetic patients receiving NAC. We believe that NAC offers a new treatment strategy for patients with CLI undergoing lower extremity amputation with the intent to improve tissue perfusion, healing, and reduce morbidity and mortality associated with lower limb amputation.

Study Objectives

Primary Aim 1

Determine whether NAC can affect major lower extremity amputation stump perfusion by POD (Post-operative Day) 5

Primary Aim 2

Determine whether NAC can affect major lower extremity stump healing for 30 days following amputation.

Secondary Aim

Determine the effect size in diabetic patients that is necessary to power a larger clinical trial to determine whether NAC treatment can improve tissue perfusion and healing at major lower extremity amputation stumps.

Rationale for the Selection of Outcome Measures

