In this pilot clinical study we propose to conduct a prospective, randomized, double-blinded, placebo-controlled clinical trial, in 50 human subjects with CLI who have undergone a major (above-knee or below-knee) lower extremity amputation. 25 patients will receive NAC 1200mg intravenously twice a day for 6 consecutive days following amputation. 25 patients will receive placebo saline intravenous infusion twice a day for 6 days following amputation. Post-amputation patients will be monitored for specific anthropometric parameters and stump perfusion assessments (using laser-assisted fluorescent angiography and transcutaneous oxygen pressure measurement). **The primary study endpoints are to determine if lower extremity stump healing and perfusion are affected by perioperative NAC administration. A secondary endpoint will be to determine the effect size that would be necessary to power a larger clinical trial to determine whether NAC treatment can affect tissue perfusion and healing at major lower extremity amputation stumps in patients with CLI.**

Subject Selection and Withdrawal

Inclusion Criteria

Inclusion criteria for recruited subjects will be as follows:

- Subject undergoing elective major (above-knee or below-knee) lower extremity amputation for CLI
- Both male and female patients
- All ethnic groups
- Between of the ages of 30-90 years old

1.a Exclusion Criteria

Exclusion criteria for patients will be as follows:

- Pregnant women, and women who are breastfeeding
- Known history of end-stage liver disease
- Severe asthma
- Heavy alcohol consumption (male > 2 drinks per day and women > 1 drink per day)
- Individuals actively receiving chemotherapy.

- Anticipated enrollment in another study that investigates another drug agent within 30 days from enrollment in this study.
- Patients receiving carbamazepine.
- Severe anemia (HCT < 22).
- Allergy to either NAC or ICG

All inclusion and exclusion criteria will be verified from patient chart in Epic and through self report and/or LAR report; in particular, alcohol consumption and participation in another drug research study to obtain the most current information. **Email correspondence between RC, PI, and other study team members regarding patient enrollment may be included in the subjects chart to serve as a real time documentation of PI's approval to enroll participant, in addition to signature in CRFs.**

Ethical Considerations

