- **Day 0 (Day of Operation):** If possible and/or equipment available, obtained prior to the operation at the anticipated level of the amputation.
- **Postoperative Day3:** If possible and/or equipment available, obtained following dressing removal at bedside in the inpatient hospital unit.
- **Postoperative Day5:** If possible and/or equipment available, also obtained at bedside in the inpatient hospital unit if the patient is still in-house.

[figure not shown]
Contraindications to Measurement:

- Patient refusal/inability to participate in measurement before or during data collection
- Patient SpO₂ < 92%, Patient is febrile >38°C, unstable vitals
- Patient unable to lie supine for at least 20 minutes during measurement collection
- Patient unable to breathe normobaric oxygen
- *A contraindication to TcPO₂ measurements does not exclude the patient from other measurements within the study protocol

Protocol Steps:

1. Ensure patient meets the eligibility criteria above.
2. Keep patient covered, and expose the anticipated amputation site or at the amputation stump. Do not elevate the site throughout the measurement collection.
3. Select 4 collection sites as follows:
 1. 3 sites on the anticipated amputation site the stump site, one per section. (Figure 1)
 2. 1 control site on the left anterior chest in indicated on figure. (Figure 1)
4. Electrodes will be placed as per TCM Manual instructions, replicated below with the following specifications:
 1. Temp. set to 45°C.
 2. Do not place probes on scar tissue or dermatologically compromised sites.
 3. Do not place probe over bone.
5. After 15-20 minutes, record the TcPO₂ numbers in all 4 sites. Mark the location of the sites for future measurements to ensure a consistent location for measurement and control (days 2 and 4).
6. Remove probes from patients.

Figure 1

listed

or at

area

Data Analysis:

After TcPO₂ measurements have been collected, the 3 amputation site measurements will be averaged to calculate a mean TcPO₂. The control site measurement on the operated leg will be used to calculate a Regional perfusion index (Mean TcPO₂ / Chest/Control TcPO₂). The non-operated leg measurement site (compared against the operated site) will be used to determine if lower TcPO₂ values in the amputation site are due to regional or systemic oxygenation.

How to place an electrode

Step	Action
------	--------

1. Calibrate the tcpO₂ electrode.

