 1. CBC
 2. BMP
 3. HbA1C (Maybe obtained at some point during the course of the 6 day study if the patient did not have a value obtained within 3 month prior to the amputation)
 4. Pre-albumin (May be obtained at some point during the course of the 6 day study if the patient did not have a value obtained within 1 week prior to the amputation)
2. Research laboratory evaluation
 1. One sample within 12 hours from the time of the amputation operation, if possible
 2. One sample within 12 hours prior to discharge from the hospital or by POD5, if possible
 3. Samples will be taken to the research laboratory to evaluate:
 1. Serum Insulin level
 2. Serum Thiol Level
 3. Serum L-Cysteine level
 4. Serum lipidomics
 5. Serum nicotine and cotinine levels
 6. Other essential plasma/serum proteins or biomarkers

Contraindications to Measurement:

- Patient refusal/inability to participate in measurement before or at time of data collection (*a contraindication to anthropometric measurements does not exclude the patient from other measurements within the study protocol*).
- Severe anemia (Hematocrit < 22), that develops following enrollment in the study.

Data Analysis:

Anthropometric data will be analyzed to determine its effects on patient amputation stump healing score, qualitative peak perfusion, and/or quantitative peak perfusion.

D. MRI Measurements

Location of Procedure:

- Center for Clinical Imaging Research

Time of Data Collection:

- Postoperative Day 4, If possible and/or equipment available and if the patient is still in-house.

Contraindications to Measurement:

- Patient refusal/inability to participate in measurement before or during data collection
- Patient unable to lie supine for at least 30 minutes during measurement collection
- Contraindication to MR scanning such as intracranial vascular clips, pacemaker or intraocular metal.
- Patient is hemodynamically unstable, pregnant, are claustrophobic.

MRI Procedural Steps:

1. The patient is asked to lie supine on a narrow bed in the MRI scanner. An MRI scanner is a large donut-shaped machine that is used by thousands of hospitals to make pictures of various parts of the body. The patient is given ear plugs or earphones to dampen the loud noise the scanner makes when taking pictures. The patient is also given a squeeze ball which can activate an alarm at the scanner operator's console, so the patient can let the operator know to have a question or need assistance.

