 23. Kapp, M.B., *Ethical and legal issues in research involving human subjects: do you want a piece of me?* J Clin Pathol, 2006. **59**(4): p. 335-9.
 24. Holdiness, M.R., *Clinical pharmacokinetics of N-acetylcysteine.* Clin Pharmacokinet, 1991. **20**(2): p. 123-34.

STATISTICAL ANALYSIS PLAN

**Protocol Title: N-Acetyl-Cysteine for Healing of
Amputation Stumps in the Setting of Diabetes**

NCT03253328

**Protocol Version 11.0
Date: March 26, 2020**

Statistical Plan

Sample Size Determination and Power

The purpose of this study is to obtain sufficient preliminary data to determine the sample size necessary for a future large definitive clinical trial. For this pilot study, we plan to enroll 25 patients in each group, allowing for a dropout rate of 10% per group.

We emphasize that effect size (the expected difference in primary outcome between the treatment and control groups) should not be determined by the pilot study. Rather it is determined by the minimum clinically important difference. However, the effect size from the pilot give us some ideas about possible achievable difference.

Interim Monitoring and Early Stopping

An interim analysis will be conducted once >30 patients are enrolled in the study. Analysis will focus on determining differences between NAC and control group. Interim analysis will help determine early differences between the study groups and safety profile of study intervention. The investigators may end the study early depending on study findings, safety profile of the data, and/or if data is adequate for a peer-reviewed publication.

Analysis Plan

Data analysis include (1) the partition of variation of outcome measurements into within and between patient components to obtain standard deviation of measurements, intra-class correlation of the measurements, (2) use of appropriate regression model (GEE or mixed effect regression) to compare the outcome measurements between two groups, while accounting for the intra-class correlation. Interpretation of analysis should be made within the context of a pilot study where we have a pre-specified hypothesis but do not have power analysis for testing the hypothesis.

Statistical Methods

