One of the main study outcomes (and in the future large study) is the stump perfusion assessment, which is a continuous variable measured three times (D0, D3, and D5) after treatment. Based on this longitudinal repeated measurement study design, the preliminary data needed for designing future study include: (1) variance of single measurement, (2) covariance (correlation) among the repeated measurements over time within an individual, (3) level of outcome measurements in patients with and without the treatment.

Missing Outcome Data

Not applicable

Unblinding Procedures

The BJH Investigational Pharmacy will maintain a record of each patient's medical record number and to which arm of the study they were assigned. No member of the vascular surgery investigational team will have access to this information. This will serve to maintain blinding and reduce any unwanted during the trial and subsequent analysis of collected data. Un-blinding of patient data will occur during the interim analysis, and at the end of the study. For un-blinding the pharmacy will then un-blind the study to the investigators such that appropriate conclusions can be made regarding the efficacy of the investigational agent.

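### Primary Aim 1 names no perfusion measure or time contrast, so the primary result could be selected after unblinded group differences are seen; the SAP also counts the pre-drug day 0 reading as after treatment

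*Combined protocol and SAP*

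**What the plan says.** **The aim.** Study Objectives, Primary Aim 1, reads: "Determine whether NAC can affect major lower extremity amputation stump perfusion by POD (Post-operative Day) 5". It gives no instrument, variable or contrast.

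**The methods.** Overview or Design Summary says stump perfusion is assessed "using laser-assisted fluorescent angiography and transcutaneous oxygen pressure measurement", with neither ranked first.

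**The variables.** Four candidates can be found.
- Schedule of Measurements, section B (TcPO2), Data Analysis: "the 3 amputation site measurements will be averaged to calculate a mean". That mean is then divided by the chest control value to give a regional perfusion index.
- Section C (Anthropometric Measurements), Data Analysis, plans to examine how anthropometric data bear on a stump healing score, "qualitative peak perfusion, and/or quantitative peak perfusion". Neither peak perfusion variable is defined anywhere, and the sentence does not mention LAFA.

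**The analysis.** SAP, Statistical Methods, calls the stump perfusion assessment one of the main outcomes, "which is a continuous variable measured three times (D0, D3, and D5) after treatment". SAP, Analysis Plan, compares the groups by GEE or a mixed model and names no contrast. No alpha, hierarchy or multiplicity rule is given.

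**Timing of day 0.** LAFA is done in the operating room after the amputation (section A). The first infusion follows within three hours of leaving the operating room (Treatment Regimen). For TcPO2, day 0 is "If possible and/or equipment available, obtained prior to the operation at the anticipated level of the amputation".

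**The interim.** SAP, Interim Monitoring and Early Stopping, plans an analysis of group differences once more than 30 patients are enrolled. The investigators may stop, among other grounds, "if data is adequate for a peer-reviewed publication". Unblinding Procedures releases the treatment codes to the investigators at that point.

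**The concern.** An aim that any of several variables could answer, in a plan that does not say which one does, leaves the choice to be made later. Here later can mean after the investigators have seen the data by arm, at a look where publishability is a ground for stopping. The reported perfusion effect could then come from whichever measure happened to look best.

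The pilot exists to supply variances, correlations and outcome levels for a larger trial, and the Secondary Aim asks it for an effect size. Those figures are only useful if they belong to a measure chosen for reasons other than its observed difference.

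The day 0 wording is a second problem. A reading taken before the first infusion cannot carry a drug effect. If it is modelled as one of three post-treatment outcomes, a common group effect averages a null contrast with the informative ones.

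**Working it through.** The documents give no alpha, effect size, SD or error rate for Aim 1, so there is no stated figure to reproduce. The only related number is 25 per group with 10% dropout: 25 × 0.9 = 22.5, or about 22 evaluable per arm.

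**1. Chance of at least one nominal finding**

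Assumptions: no true effect, each test two-sided at 0.05, and test statistics standard normal with equal pairwise correlation ρ. Neither the 0.05 nor ρ is in the documents; ρ is varied from 0.3 to 0.7.

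For independent tests the chance is 1 − 0.95^k:
- k = 4: 1 − 0.95⁴ = 18.5%
- k = 8: 1 − 0.95⁸ = 33.7%

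With correlation, by simulation (300,000 draws):

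| Tests | ρ = 0.3 | ρ = 0.5 | ρ = 0.7 |
|---|---|---|---|
| 4 measures, one test each | 17.3% | 15.6% | 13.1% |
| 4 measures × POD 3 and POD 5 | 29.9% | 25.0% | 19.1% |

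About half of these results would favour NAC. For four tests the figure is 8.7% at ρ = 0.3 and 7.7% at ρ = 0.5.

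Equal correlation is a simplification, because mean TcPO2 is the numerator of the index. With two close pairs (0.8 within a pair, 0.3 across pairs, 0.6 between days) the eight-test figure is 24.2%, inside the range above.

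These figures leave out the interim look. An unadjusted look at 30 of 50 patients alone takes a single test from 5% to about 8%.

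**2. Effect of selection on the estimate**

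With 22 per arm, the standard error of a standardised mean difference is about √(2/22) = 0.302. The expected largest of four equicorrelated null statistics is 1.03 × √(1 − ρ).
- ρ = 0.3: 1.03 × 0.837 × 0.302 = 0.26 SD
- ρ = 0.7: 1.03 × 0.548 × 0.302 = 0.17 SD

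So the best-looking of four measures would show an apparent benefit of about 0.17–0.26 SD when there is none. Any effect of selection on the SD itself was not calculated.

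**3. Day 0 inside the outcome vector**

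If treatment means study drug, neither day 0 reading is after treatment. If it means the amputation, LAFA day 0 qualifies and TcPO2 day 0 does not. On either meaning the drug effect at day 0 is zero.

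Suppose the true group difference is 0 at D0 and δ at D3 and D5. With complete data and exchangeable correlation, a common group effect estimates (0 + δ + δ)/3 = 0.67δ. If the effect appears only at D5, it estimates δ/3 = 0.33δ.

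**The case against.** Much of the opposing case stands.

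- **The and/or phrase is not a rule for Aim 1.** It belongs to an analysis of how anthropometric data relate to healing and perfusion, and it does not mention TcPO2. A reader might infer that the plan lets Aim 1 be claimed on any of four measures at either day. No text says so. The documents are silent, and they do not prevent selection.
- **The SAP model does not single out LAFA.** A reader might infer that only quantitative LAFA fits it. Mean TcPO2 and the regional perfusion index are also continuous and scheduled at day 0, POD 3 and POD 5, so both can go into a GEE or mixed model. Only the word continuous counts against a qualitative score. Equipment availability is a missing-data matter.
- **Eight separate tests are not planned.** A repeated-measures regression uses the days together. One test per measure is closer to the plan, so 13–17% is the leading figure. The higher range applies only if the days are tested separately, which the missing contrast leaves open.
- **This is a pilot.** The SAP says that there is no power analysis for testing the hypothesis and that effect size should come from the minimum clinically important difference. That weakens any claim that a selected effect passes straight into the next trial. It does not remove the problem: the same SAP paragraph lets the pilot effect inform what is achievable, the Secondary Aim asks for an effect size, and a clinically important difference or planning SD cannot be set for an unnamed measure.
- **Stopping for publishability is its own problem.** It matters here only because it puts unblinded results before the investigators while the endpoint is still open.

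**Conclusion.** The concern holds as a gap in the plan. Aim 1 is not tied to one measure or one contrast, nothing ranks the candidates, and investigators see results by arm before the end. The primary perfusion result could therefore be selected after the data are seen.

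Under no effect, the chance of at least one nominally significant result is 13–17% for one test on each of four measures, and 19–30% if both days are tested separately. About half of these would favour NAC. The figures rest on an assumed two-sided 0.05 and assumed correlations of 0.3–0.7, and they exclude the interim look. They do not support calling a chance finding likely, and they do not show that anyone intends to select.

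Separately, the SAP's description of D0 as after treatment conflicts with the measurement and infusion schedules. Read literally, it would shrink an effect present at both POD 3 and POD 5 to about two thirds of its size.

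**What to change.** Add to the SAP, before any unblinding:

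1. The Aim 1 primary measure is quantitative peak LAFA perfusion, with a one-line definition (region of the stump, unit, how the peak is taken).
2. The primary comparison is NAC versus placebo at one named contrast, for example POD 5, from a mixed model that also uses POD 3. POD 0 LAFA enters as a baseline covariate, not as an outcome, and the words placing D0 after treatment are corrected.
3. Qualitative perfusion, mean TcPO2, the regional perfusion index and other time points are supportive and reported with confidence intervals.
4. The SD and correlations for the next trial are taken from the primary measure.

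Choosing LAFA follows the documents' own lean: patients who cannot have POD 0 LAFA are withdrawn before dosing (Early Withdrawal of Subjects), and MR perfusion is described as an adjunct to LAFA. It remains a choice for the investigators to confirm.

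The cost is a few SAP sentences and no new data. There are two downsides. POD 5 LAFA is not done in patients already discharged, and Table 1 gives POD 5 as the anticipated discharge day, so the POD 5 estimate will lean on POD 3 data through the mixed model. The Missing Outcome Data section, now marked not applicable, should say so. TcPO2 also becomes supportive only.

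A single final test at 0.05 then has a 5% error rate. The interim look still needs its own rule, since without one that rate is about 8%.
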